## **16. Statistical Considerations**

Because this is a pilot study, no formal sample size/power calculation is required. However, with 12 patients each cohort, an exact binomial (Clopper-Pearson) 95% confidence interval for the toxicity proportion (i.e., primary endpoint) can be constructed to have a width of approximately 45.0% (1.6%, 46.5%) (i.e., separate confidence interval for each cohort). This calculation assumes that the toxicity proportion for the incidence of non-hematologic Grade  $\geq 3$  events will be no greater than 15% in either cohort. Secondary endpoints include major response (PR/VGPR/CR), percentage of patients with deepening of response in Cohort B, duration of response, and time to progression. Given this is a pilot study with low subject enrollment and lack of power, analysis of outcomes will remain descriptive without comparison analyses between cohorts. The toxicity and major response proportions will be calculated for each cohort along with exact binomial (Clopper-Pearson) 95% confidence intervals. Duration of response and time to progression will be descriptively reported for each cohort. Assuming adequate follow-up time, Kaplan-Meier survival analysis will be used to assess progression-free survival (PFS) and overall survival (OS) in each cohort. All p-values will be two-sided with statistical significance evaluated at the 0.05 alpha level. Ninety-five percent confidence intervals for 1) the toxicity proportion, 2) the major response proportion, and 3) median PFS/OS-time and PFS/OS proportions, will be calculated to assess the precision of the obtained estimates. All analyses will

be performed in SAS Version 9.4 (SAS Institute, Inc., Cary, NC) and Stata Version 15.0 (StataCorp, College Station, TX).

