### **11. Duration of Therapy and Criteria for Removal from Study**

In the absence of treatment delays due to adverse event(s) greater than 4 weeks from scheduled dose, combination treatment may continue for 2 years with 1 year of ibrutinib monotherapy or until one of the following criteria applies:

- Disease progression,
- Intercurrent illness that prevents further administration of treatment,
- Unacceptable adverse event(s),
- Patient decides to withdraw from the study, or
- General or specific changes in the patient's condition render the patient unacceptable for further treatment in the judgment of the investigator.

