## Section 5.3.

If the investigator feels the toxicities outlined above, are likely attributed to ibrutinib dosing, daratumumab dosing may continue without being held after discussion with the study monitor. Upon recovery of  $\leq$  Grade 2, ibrutinib dosing should be the initial drug restarted. Daratumumab infusions should restart at least 7 days after ibrutinib dosing has resumed and there has been no recurrence of the toxicity.

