### **12.4.1. Daratumumab Dose Delay Management**

If dosing is delayed for either toxicity or other non-toxicity related issue then the following schedule should be followed during the specific phases of daratumumab treatment.

During the induction phase (Cycles 1 and 2) if the dose is delayed  $>3$  days then that week's dose will be considered missed and treatment will commence the following week. If a missed dose occurs during induction, then that dose will not be made up and subjects will remain on schedule.

During the consolidation phase (Cycles 3-6) if a dose is held greater than 1 week, then the next dose given should be the scheduled Day 15 dose.

During the maintenance phase Cycle 7 and beyond if a dose is delayed greater than 2 weeks then it should be resumed with the subsequent cycle on day 1.

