## **22. Data and Safety Monitoring Plan (DSMP)**

Monitoring activities will be commensurate with the nature, size and complexity of the trial in accordance with institutional policies and will be determined after IRB and Data Safety Monitoring Board (DSMB) review of the protocol immediately prior to study activation. For this study we will utilize a Weill Cornell Medicine DSMB.

We will evaluate safety of combination therapy after 12 subjects have been enrolled onto the protocol and completed 8 weeks of combination induction therapy. The study team will review all subject data at this specified time point and provide a written report to the DSMB for review. Stopping rules will be employed in this study based on observed toxicities from monotherapy trials in subjects with multiple myeloma receiving daratumumab or WM subjects receiving monotherapy ibrutinib. For purposes of this safety analysis, each subject will be assessed individually and toxicities tabulated. Only toxicities occurring within the first 8 weeks of combination treatment will be considered for potential study termination.

In monotherapy daratumumab or ibrutinib studies, Grade 3 or greater non hematologic toxicities were rare with the most common event being pneumonia noted in 6% of subjects respectively for daratumumab and ibrutinib (data from prescribing inserts). Grade 3 or greater hematologic toxicities when restricted to anemia, thrombocytopenia, or neutropenia were noted in up to 20% of subjects treated with daratumumab monotherapy and up to 19% in subjects treated with ibrutinib monotherapy.

Based on these observed events we will stop the study if 5 of the first 12 subjects enrolled experience a Grade 3 or greater, toxicity (heme or non-heme) which leads to a study drug hold greater than 28 days or leads to either study drug discontinuation within the first two months of treatment. Any drug hold that occurs within the first 8 weeks but extends beyond the initial 8 week monitoring period will be followed for a full 28 days. For a toxicity to be included in this analysis, the toxicity must be considered due to the study drug per investigator assessment. Accrual will be held upon enrollment of the 12th evaluable subject until they have been observed through induction and the study team in consultation with the DSMB have made a determination regarding additional enrollment, this study hold is anticipated to last approximately 3 months.

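### Section 22 describes the 12 subjects of its safety review, stopping count and accrual hold in three ways, leaving lead-in dropouts and the review timing unsettled (minor: Section 16's planning interval is unattainable with 12 patients)

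*Combined protocol and SAP*

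**What the plan says.** Section 22 (Data and Safety Monitoring Plan) refers to 12 subjects in three sentences.

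- **Review timing:** safety is evaluated after 12 subjects have been "enrolled onto the protocol and completed 8 weeks of combination induction therapy".
- **Stopping count:** "we will stop the study if 5 of the first 12 subjects enrolled experience a Grade 3 or greater, toxicity (heme or non-heme"). A toxicity counts if it is one "which leads to a study drug hold greater than 28 days or leads to either study drug discontinuation within the first two months of treatment", and if the investigator judges it due to study drug.
- **Accrual hold:** "Accrual will be held upon enrollment of the 12th evaluable subject until they have been observed through induction", and until the study team and DSMB have decided on further enrollment.

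Section 22 does not define evaluable. The Synopsis (Methodology) gives two senses: completing the 8 weeks of induction for response, and receiving one daratumumab dose for toxicity. Section 14.2 repeats the distinction. Section 22 also restricts study termination to toxicities in the first 8 weeks of combination treatment. Under Section 9.3, Cohort A takes ibrutinib alone for one 28-day cycle before combination treatment starts.

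Section 16 gives the precision of the primary endpoint for 12 patients per cohort. At an assumed toxicity proportion of no more than 15%, the Clopper-Pearson 95% interval "can be constructed to have a width of approximately 45.0% (1.6%, 46.5"%).

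**The concern.** This is the only numerical rule for halting the study, and Section 6.2.5 says daratumumab had not been studied clinically in this disease. The team should be able to apply such a rule without inference. With three descriptions of the 12, it is unclear who fills the places, when the review falls due, and when accrual stops and restarts. A place taken by someone who cannot have a counted event makes the rule less likely to trigger at the same true toxicity rate.

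The Section 16 interval is the only precision figure given for the primary endpoint, and it is not one that the trial could report.

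**Working it through.** **1. Lead-in dropouts and the count.** Section 8.1 allows no study medication before registration is confirmed, so a Cohort A patient in the lead-in is already enrolled. The Synopsis (Treatment Administration) requires a Grade 3 or greater toxicity in Cohort A to resolve to Grade 1 or less before daratumumab is added. Some lead-in patients may therefore never reach combination treatment. Such a patient is one of the first 12 enrolled but has no first 8 weeks of combination treatment in which a counted event could fall.

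With m such patients among the 12, P(stop) = P(X ≥ 5), where X ~ Binomial(12 − m, p). The documents give no rate p for the counted event and no lead-in dropout rate. Both are assumptions, shown as a range:

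| True event rate p | m = 0 | m = 1 | m = 2 |
|---|---|---|---|
| 15% | 2.4% | 1.6% | 1.0% |
| 20% | 7.3% | 5.0% | 3.3% |
| 30% | 27.6% | 21.0% | 15.0% |
| 40% | 56.2% | 46.7% | 36.7% |
| 50% | 80.6% | 72.6% | 62.3% |

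At 40%, one lead-in dropout costs 56.2 − 46.7 = 9.5 points and two cost 56.2 − 36.7 = 19.5 points.

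**2. Review timing against the accrual hold.** Suppose accrual is held at 12 subjects and one discontinues during induction. Then 12 − 1 = 11 can complete 8 weeks of combination treatment, and nobody is enrolled to replace the twelfth. Read literally, the review timing is never reached. The accrual sentence has no such problem, because it asks only that the subjects be observed through induction. The two sentences therefore disagree about when the review is due.

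**3. The time window.** The stopping sentence refers to the first two months of treatment, while the preceding text refers to the first 8 weeks of combination treatment. If two months is taken as 56 days from the start of ibrutinib, a Cohort A patient has 56 − 28 = 28 days of combination treatment in the window, not 56. The word *only* in the termination sentence points to the combination window.

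**4. Section 16 interval.** Inputs from Section 16: n = 12, 15%, Clopper-Pearson, 95%. Lower limit = Beta quantile 0.025 with parameters (x, n − x + 1). Upper limit = Beta quantile 0.975 with parameters (x + 1, n − x).

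The plan's figure uses x = 0.15 × 12 = 1.8. Beta(1.8, 11.2) gives 1.57% and Beta(2.8, 10.2) gives 46.54%, a width of 44.97 points. The stated interval is reproduced, but 1.8 is not an observable count. Whole counts give:

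| Events | 95% interval | Width (points) |
|---|---|---|
| 0/12 | 0% to 26.5% | 26.5 |
| 1/12 | 0.2% to 38.5% | 38.3 |
| 2/12 | 2.1% to 48.4% | 46.3 |
| 3/12 | 5.5% to 57.2% | 51.7 |

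The maximum width is 57.8 points, at 6/12. Weighting each width by its Binomial(12, 0.15) probability gives an expected width of 42.9 points.

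**The case against.** A reader might infer that Section 22 drops the very patients the rule exists to count, because someone who stops for toxicity has not completed 8 weeks. The documents do not support that. The stopping count has one stated denominator, the first 12 enrolled. The rule counts discontinuations, so restricting it to completers would defeat it. The team reviews all subject data, and a hold that runs past week 8 is followed for its full 28 days.

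A reader might also take evaluable in the accrual sentence to mean response-evaluable. If induction were already complete, nothing would remain to be observed through induction, so the toxicity sense is the only workable one.

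Nor can it be said that most counted patients are non-completers. Section 11 lets combination treatment continue only "In the absence of treatment delays due to adverse event(s) greater than 4 weeks from scheduled dose, combination treatment may continue for 2 years" or until a removal criterion applies, which points towards ending treatment after a long hold. But Section 12.4.1 says "If a missed dose occurs during induction, then that dose will not be made up and subjects will remain on schedule", so a held patient might still complete induction by the calendar. The timing problem is therefore claimed here only for discontinuations.

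It is also fair to say that a sensible team would hold the review once all 12 had passed week 8. Early stoppers would not be hidden: the DSMB receives a written report, and serious events go to the company within 24 hours (Section 20.1). That limits the weight of the point. It does not settle whether a lead-in dropout holds a place, and it leaves the timing sentence at odds with the accrual sentence.

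On Section 16, a reader might infer an arithmetic error, an optimistic width or an inadequate sample. None follows. The figure reproduces from its inputs and is labelled approximate. Its 45.0 points lie between the expected 42.9 and the 46.3 at 2/12. The planned analysis uses the exact interval on the observed count, and Section 16 says the sample size rests on no formal calculation.

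**Conclusion.** The point holds at low to moderate severity, as an inconsistency in Section 22. Early stoppers stay in the count on the natural reading.

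Two defects remain when the text is followed as written. First, a Cohort A lead-in dropout fills one of the 12 places without being able to have a counted event. At an assumed 40% event rate, this lowers the chance of stopping from 56.2% to 46.7% with one dropout or 36.7% with two. These figures assume independent patients with a common event rate, and the documents do not say how often lead-in dropout would occur. Second, a review timed to 12 completers cannot be reached under the accrual hold if any of the 12 discontinues in induction; this needs no assumed rate. The two descriptions of the time window need only a wording correction.

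The Section 16 interval is a minor matter of presentation: an unattainable planning figure with no effect on the 12 per cohort.

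**What to change.** **Section 22.**
- Use one description of the 12 for the count, the review timing and the accrual hold, reconciled with the Synopsis (Methodology) and Section 14.2. The plan's own toxicity-evaluable definition, at least one daratumumab dose, would serve.
- In the timing sentence, replace completion of 8 weeks with the plan's own idea of subjects having been observed through induction.
- State whether a Cohort A lead-in dropout is replaced among the 12. Say also how the accrual hold treats a Cohort A subject still in the lead-in, whose first daratumumab dose comes 28 days after ibrutinib starts.
- Reconcile the two-month window with the 8-week combination window.
- Leave the threshold of 5 as it is.

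**Section 16.** Replace (1.6%, 46.5%) with the attainable intervals for 0/12 to 3/12 and the expected width of 42.9 points at a true 15%.

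**Cost.** Wording and one small table; the planned total of 24, the visits and the data collected are unchanged. If lead-in dropouts are replaced among the 12, the accrual hold comes one enrolled subject later for each. The width quoted at 2/12 would be 46.3 − 45.0 = 1.3 points larger than the present figure.

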## **17. Reporting and Exclusions**

### **17.1. Adverse Events and Reporting Requirements**

Adverse event (AE) monitoring and reporting is a routine part of every clinical trial. The investigator will be required to provide appropriate information concerning any findings that suggest significant hazards, contraindications, side effects, or precautions pertinent to the safe use of the drug or device under investigation. Safety will be monitored by evaluation of adverse events reported by patients or observed by investigators or research staff, as well as by other investigations such as clinical laboratory tests, x-rays, electrocardiographs, etc.

### **17.2. Adverse Event Definition**

An adverse event is any untoward medical occurrence in a clinical study subject administered a medicinal (investigational or non-investigational) product. An adverse event does not necessarily have a causal relationship with the treatment. An adverse event can therefore be any unfavorable and unintended sign (including an abnormal finding), symptom, or disease temporally associated with the use of a medicinal (investigational or non- investigational) product, whether or not related to that medicinal (investigational or non-investigational) product. (Definition per International Conference on Harmonisation [ICH]). This includes any occurrence that is new in onset or aggravated in severity or frequency from the baseline condition, or abnormal results of diagnostic procedures, including laboratory test abnormalities.

### **17.3. Adverse Events of Special Interest for Daratumumab (DARZALEX®)**

Adverse events of special interest are events that Janssen Scientific Affairs, LLC is actively monitoring as a result of a previously identified signal (even if non-serious). These adverse events are:

- Infusion reactions:  $\geq$  grade 3
- Infections:  $\geq$  grade 4
- Cytopenias:  $\geq$  grade 4
- HBV Reactivation
- Visual Disturbance
- Other malignancies

Any Adverse Event of Special Interest that is to be reported to the COMPANY should be recorded on a Serious Adverse Event Report Form and be reported to the COMPANY within 24 hours of knowledge of the event.

#### **17.4. Adverse Events of Special Interest for Ibrutinib (Imbruvica®)**

Adverse events of special interest are events that Janssen Scientific Affairs, LLC is actively monitoring as a result of a previously identified signal (even if non-serious). These adverse events are:

- *Major Hemorrhage*

Major hemorrhage is defined as any hemorrhagic event that is Grade 3 or greater in severity or that results in 1 of the following: intraocular bleeding causing loss of vision, the need for a transfusion of 2 or more units of red cells or an equivalent amount of whole blood, hospitalization, or prolongation of hospitalization.

- *Intracranial Hemorrhage*

Any intracranial hemorrhage adverse event, including subdural hematoma/hemorrhage, epidural hematoma/hemorrhage and intracerebral hemorrhage, of any grade severity, will be captured as an event of special interest.

- *Other Malignancies*

In addition to all routine AE reporting, all new malignant tumors, including solid tumors, skin malignancies and hematologic malignancies, are to be reported for the duration of study treatment and during any protocol-specified follow-up periods including post-progression follow-up for overall survival.

Any Adverse Event of Special Interest that is to be reported to the COMPANY should be recorded on a Serious Adverse Event Report Form and be reported to the COMPANY **within 24 hours of knowledge of the event.**

#### **17.5. Individual Case Safety Report**

A valid ICSR must contain the four minimum criteria required to meet regulatory reporting requirements.

- an identifiable subject (but not disclosing personal information)
- an identifiable reporter (investigational site)
- a Janssen medicinal product
- an adverse event, outcome, or certain special situations

The minimum information required is:

- suspected Janssen medicinal product (doses, indication)
- date of therapy (start and end date, if available)
- batch or lot number, if available
- subject details (subject ID and country)
- gender

- age at AE onset
- reporter ID
- adverse event detail (AE verbatim in English), onset date, relatedness, causality, action taken, outcome, (if available)

## **17.6. Product Quality Complaint**

A product quality compliant is defined as any suspicion of a product defect related to a potential quality issue during manufacturing, packaging, release testing, stability monitoring, dose preparation, storage or distribution of the product, or delivery system. Not all PQCs involve a subject. Lot and batch numbers are of high significance and need to be collected whenever available.

Examples of PQC include but not limited to:

- Functional Problem: e.g., altered delivery rate in a controlled release product
- Physical Defect: e.g. abnormal odor, broken or crushed tablets/capsules
- Potential Dosing Device Malfunction: e.g., autoinjector button not working, needle detaching from syringe
- Suspected Contamination
- Suspected Counterfeit

## **17.7. Serious Adverse Event (SAE)**

A serious adverse event based on ICH and EU Guidelines on Pharmacovigilance for Medicinal Products for Human Use is any untoward medical occurrence that at any dose:

- Results in death
- Is life-threatening  
(The subject was at risk of death at the time of the event. It does not refer to an event that hypothetically might have caused death if it were more severe.)
- Requires inpatient hospitalization or prolongation of existing hospitalization
- Results in persistent or significant disability/incapacity
- Is a congenital anomaly/birth defect
- Is a suspected transmission of any infectious agent via a medicinal product
- Is medically important\*

\*Medical and scientific judgment should be exercised in deciding whether expedited reporting is also appropriate in other situations, such as important medical events that may not be immediately life threatening or result in death or hospitalization but may jeopardize the subject or may require intervention to prevent one of the other outcomes listed in the definition above. These should usually be considered serious.

**NOTE: DEATH FOR ANY REASON SHOULD BE REPORTED AS A SERIOUS ADVERSE EVENT.**

### **17.7.1. Hospitalization**

For reports of hospitalization, it is the sign, symptom or diagnosis which led to the hospitalization that is the serious event for which details must be provided.

Any event requiring hospitalization or prolongation of hospitalization that occurs during the study must be reported as a serious adverse event, except hospitalizations for the following:

- Hospitalizations not intended to treat an acute illness or adverse event (e.g., social reasons such as pending placement in long-term care facility)
- Surgery or procedure planned before entry into the study. [Note: Hospitalizations that were planned before the start of data collection and where the underlying condition for which the hospitalization was planned has not worsened will not be considered serious adverse events. Any adverse event that results in a prolongation of the originally planned hospitalization is to be reported as a new serious adverse event.]
- [For convenience the investigator may choose to hospitalize the subject for the duration of the treatment period.]

### **17.7.2. Life-Threatening Conditions**

Disease progression should not be recorded as an adverse event or serious adverse event term; instead, signs and symptoms of clinical sequelae resulting from disease progression/lack of efficacy will be reported if they fulfill the serious adverse event definition.

## **17.8. Unlisted (Unexpected) Adverse Event/Reference Safety Information**

An adverse event is considered unlisted if the nature or severity is not consistent with the applicable product reference safety information. For a medicinal product(s) with a marketing authorization, the expectedness of an adverse event will be determined by whether or not it is listed in the applicable product information.

<http://www.darzalex.com/shared/product/darzalex/darzalex-prescribing-information.pdf>

For DARZALEX™ (daratumumab), the expectedness of an adverse event will be determined by whether or not it is listed in the Investigator's Brochure

